14.0 Withdrawal of Subjects*

14.1 We do not anticipate subjects being withdrawn from the study without their consent.

14.2 n/a

15.0 Risks to Subjects*

15.1 Risks:

Risks are fairly minimal. There is a chance that some parents or children may experience mild, transient distress during parts of the assessments. All questions (self-report) are the type typically asked during a routine psychological or medical evaluations. If necessary, the assessment can be interrupted or terminated. The family (parent and patient) will be clearly informed that they are free to terminate participation at any point in the protocol.

The EEG and startle recording is completely non-invasive. The EEG will be recorded with an ActiveTwo EEG recording system, which does not require abrading the skin. There is the possibility that some participants will experience mild, temporary itching or tingling sensation in response to the electrode cap or electrode gel.

Informed consent and assent will be obtained prior to participation, and risks will be explained carefully to the participants' parent. An additional "Coronavirus Information Sheet" will be provided to participants in order to address any concerns about the steps being taken by research staff.

All information with identifying information collected during the project will be kept in a locked storage cabinet to which only [name] and the study coordinator will have access. All data will be stored separately from identifying information and will be password protected. No names will be maintained in data

records; rather, information will be coded by ID numbers only. Each individual will receive a unique I.D. number thereby allowing handling of data on all subjects without using individual names. PI [name] will be responsible for monitoring the maintenance of confidentiality. In the event of a breach of confidentiality, he will inform the subject and his/her parents that the breach occurred; any breaches of confidentiality will be reported to the Institutional Review Board. Codifying participants by unique identifiers is an extensive practice that is highly efficient at protecting anonymous participation. No individual child or family will be identified in any publications or presentations of the research findings.

Upcoming procedures are repeatedly explained to the children and their parent, giving them a sense of control over what is happening in their environment. Rather than closed yes/no questions, open-ended questions with regard to comfort and well-being will be used throughout the procedures to give subjects the opportunity to voice any concerns or discomfort. Subjects will also be given the opportunity to ask questions regarding the research procedures at any time during the protocol.

Although we don't expect it frequently, some subjects may endorse suicidality or increased risk for suicidality; in this event, safety assessments will be conducted and, when necessary, appropriate consultation with [name] will be held to determine disposition. [name] is a clinical psychologist, with an office on the same floor where the research will take place. In the event that a participant is in imminent danger to themselves, their parents will be informed. The participant and [name] will meet with the subject and their parent to establish a safety plan – which may include transporting the child to the emergency room for further psychological evaluation or a referral for follow-up evaluation with an outside provider. Referrals will be on hand and can be provided. We will use validated procedures for suicide assessment, specifically the structured interview recommended by Joiner et al. (1999) & Chu et al. (2015), and use the following method to designate risk severity (refer to ABHC Suicide Risk Assessment form for detailed information on the assessment):

1. An individual's risk for suicide is designated nonexistent if he or she has no current suicidal symptoms, no history of suicide, and no or few other risk factors. 2. Risk for suicide is considered mild if the individual is a multiple attempter with no other risk factors or is a non-multiple attempter experiencing suicidal ideation of limited intensity and duration, no or mild resolved plans and preparation, and no or few other risk factors.

3. An individual is designated at moderate risk if he or she is a multiple attempter with any other significant risk factor. A non-multiple attempter with moderate to severe resolved plans and preparations or moderate to severe suicidal desire and ideation accompanied by at least two other risk factors is also considered to be at moderate risk for suicide.

4. A multiple attempter with two or more risk factors or a non-multiple attempter with moderate to severe symptoms of resolved plans and preparations

accompanied by one other risk factor is designated at severe risk for suicide. 5. An individual is at extreme risk for suicide if he or she is a multiple attempter with severe resolved plans and preparation or is a non-multiple attempter with resolved plans and preparations and two or more other risk factors. Once an individual has been assessed for suicide risk, we will take the following actions, as suggested by Joiner et al. (1999) and Chu et al. (2015): In addition, if children and/or their parents endorse experiencing significant psychological distress (e.g., significant anxiety or depression) during any portion of the study, the participants will be offered referral information for psychotherapy and/or pharmacologic treatment at Florida State University and the surrounding community. Participants who are initially enrolled in the study will not be excluded from completing study procedures if they begin receiving treatment during the study. Because information relating to child abuse may be assessed, the staff will follow federal and state child abuse reporting requirements. Participants will be informed of the need to report child abuse prior to eliciting this information. In case of any reported abuse by the child or parent, the parents will be informed about the federal mandated reporting laws, verbally and in writing. In cases where it is necessary to make a child abuse report, the family will always be informed prior to contacting any state agency, and given the option of making a self-referral to protective services.

In addition to other possible harms or discomforts related to this research, there may be risks by having participants take part in face-to-face study activities during this time of the Coronavirus emergency. Face-to-face activities and contact with other persons may increase the risk of getting Coronavirus. No one is yet quite sure how easily Coronavirus passes from person to person, how to know for certain when someone has or does not have Coronavirus, or what works best at preventing Coronavirus from spreading.

Getting Coronavirus may result in a person being isolated or quarantined at home and away from work, family and other activities. Coronavirus is a serious illness that may require medical care including hospital care, longterm disability, and even death.

Certain persons are at higher risk for severe illness from Coronavirus, and these persons are not permitted to take part in our study. Persons thought to be at higher risk include:

- Being 65 years of age or older
- Prior or current exposure to persons that have Coronavirus whether or not they know it
- Persons of any age with serious medical conditions such as diabetes, and heart, lung, kidney or liver disease, or persons who are severely obese
- Persons who have poor immunity, such as persons under cancer treatment or who have other conditions with weakened immune systems

- People who reside in or have visited nursing homes or other long-term care facilities in the 14 days prior to the lab visit.
- People who have been experiencing or have been in contact with someone experiencing flu-like symptoms such as cough, low-grade fever or high temperature (100.4°F), shortness of breath, and/or difficulty breathing in the 14 days prior to the lab visit.
- Traveled outside of the Tallahassee area in the 14 days prior to the lab visit.

All participants and study personnel will therefore be asked some questions to see who may be at risk of severe illness, or who have been exposed to Coronavirus. Even after questions are asked, participants are strongly encouraged to inform research personnel if they think that at any time before or during the study they may been exposed to Coronavirus or are at risk of severe illness. Such participants will not be permitted to participate in this study. While the study staff will take steps to protect themselves and participants from exposure to Coronavirus when they take part in face-to-face activities, there is always the chance that an individual may still be exposed.

In order to reduce exposure to Coronavirus, upon arrival in the lab we will take the temperature of all participants. If a participant has a high temperature (>100.4°F), we will wait 10 to 15 minutes take temperature a second time, to ensure accuracy. During each visit, study staff will stay at least six feet away from anyone else during research activities, excluding times when closer contact is necessary, such as when EEG is being set up, taken down, and when some computer tasks are being initiated. Study staff will conduct a maximum of one lab visit per day to reduce the chance of overlap or contamination between participants. We will also limit each lab visit to the minimum amount time and staff required to complete the study protocol. All materials will be sanitized after being utilized by participants and study staff. All disposable used items will be thrown away immediately following the lab visit. Any items that are punctured, torn, or contaminated during the visit will be rotated immediately. Study staff and participants will also be required to wear a face mask to cover their mouth and nose, wear gloves to cover their hands, wash and sanitize their hands at regular intervals; and not touch their face or anything else during study activities. If participants need protective gear such a face mask and/or gloves, study staff will provide these materials.

In addition to the risks of these Coronavirus-related harms or discomforts, this research may have risks of other Coronavirus-related harms or discomforts that are unknown at this time. Participants will be informed if any such risks are determined in the future. All participants will be reminded that if at any point they do not feel safe with the protective measures that are being taken, they can let us know and we will stop the study immediately. 15.2 n/a

15.3 n/a.

16.0 Potential Benefits to Subjects*

We have conducted the original study that utilized many of the 16.1 same measures used in the current proposal, and most children enjoy participating in the assessments, which are presented as games, and all children will win prizes and receive small gifts during the course of the tasks. The families will also receive a significant honorarium, \$60.00 for the baseline visit and \$60.00 for the follow-up assessment, and each visit should last no more than 3 hours. Providing the honorarium to the family, rather than the child, reduces the possibility that payment could be coercive—we leave it up to the parent to decide how to allocate the honorarium. If participants live more than 30 miles away, we will offer travel reimbursement of up to \$40. Periodic updates about selected research findings for the sample as a whole will be provided to subjects and their parents. Many participants derive satisfaction from knowing that they are contributing to knowledge about children's development. Although this is not a clinical sample, parents who have concerns about their child's adjustment or functioning will have the opportunity to meet with [name] (who is a clinical psychologist), and referrals will be provided if appropriate.

16.2 n/a

17.0 Data Management* and Confidentiality

Data analysis plan: AIM 1: Assess initial target engagement by 17.1 examining whether a neural marker of risk for anxiety (i.e., the ERN) in children is decreased during a single lab visit, via a brief, computerized intervention designed to target error sensitivity. We hypothesize that children who receive the intervention will display a decrease in the ERN at the first assessment, compared to children in the control condition. 1a. Assess alternate measures of target engagement. Self-report and observational measures of error sensitivity will also be decreased for parents and children who receive parent and child active interventions, respectively. AIM 2: Examine whether children in the intervention conditions display a reduction in the ERN from the initial lab assessment to the six-month follow-up assessment. We expect that children in all treatment conditions (parent/child, parent only, child only) will display a reduced ERN compared to the control group. 2a. Dissociate the impact of parent/child, parent only, versus child only treatment conditions. We hypothesize that children in the combined treatment group (parent/child) will have the greatest reduction in the ERN. 2b. Examine the impact of

utilization. We expect that parents and children who utilize the treatment materials more frequently will experience the greatest reduction in the ERN. 2c. Assess alternate measures of target engagement. We will also examine all hypotheses in relation to self-report and observed measures of parent and child error sensitivity. AIM 3: Examine whether parent/child dyads in the intervention conditions experience changes in anxiety symptoms at the six-month follow-up. We hypothesize that the dyads in the intervention conditions will experience greater changes in anxiety symptoms compared to the control group. We will also compare conditions, as well as examine the impact of utilization. In exploratory analyses, we will examine to what extent changes in the ERN and errorsensitivity relate to changes in anxiety symptoms in children.

Informed consent and assent will be obtained prior to participation, 17.2 and risks will be explained carefully to the participants' parent. All information with identifying information collected during the project will be kept in a locked storage cabinet to which only [name] and the study coordinator will have access. All data will be stored separately from identifying information and will be password protected. No names will be maintained in data records; rather, information will be coded by ID numbers only. Each individual will receive a unique I.D. number thereby allowing handling of data on all subjects without using individual names. PI [name] will be responsible for monitoring the maintenance of confidentiality. In the event of a breach of confidentiality, he will inform the subject and his/her parents that the breach occurred; any breaches of confidentiality will be reported to the Institutional Review Board. Codifying participants by unique identifiers is an extensive practice that is highly efficient at protecting anonymous participation. No individual child or family will be identified in any publications or presentations of the research findings.

Upcoming procedures are repeatedly explained to the children and their parent, giving them a sense of control over what is happening in their environment. Rather than closed yes/no questions, open-ended questions with regard to comfort and well-being will be used throughout the procedures to give subjects the opportunity to voice any concerns or discomfort. Subjects will also be given the opportunity to ask questions regarding the research procedures at any time during the protocol.

17.3 n/a.

17.4 n/a

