2.0 Objectives*

2.1 AIM 1: Assess initial target engagement by examining whether a neural marker of risk for anxiety (i.e., the ERN) in children is decreased during a single lab visit, via a brief, computerized intervention designed to target error sensitivity. We hypothesize that children who receive the intervention will display a decrease in the ERN at the first assessment, compared to children in the control condition. 1a. Assess alternate measures of target engagement. Self-report and observational measures of error sensitivity will also be decreased for parents and children who receive parent and child active interventions, respectively. AIM 2: Examine whether children in the intervention conditions display a reduction in the ERN from the initial lab assessment to the six-month follow-up assessment. We expect that children in all treatment conditions (parent/child, parent only, child only) will display a reduced ERN compared to the control group. 2a. Dissociate the impact of parent/child, parent only, versus child only treatment conditions. We hypothesize that children in the combined treatment group (parent/child) will have the greatest reduction in the ERN. 2b. Examine the impact of utilization. We expect that parents and children who utilize the treatment materials more frequently will experience the greatest reduction in the ERN. 2c. Assess alternate measures of target engagement. We will also examine all hypotheses in relation to self-report and observed measures of parent and child error sensitivity. AIM 3: Examine whether parent/child dyads in the intervention conditions experience changes in anxiety symptoms at the six-month follow-up. We hypothesize that the dyads in the intervention conditions will experience greater changes in anxiety symptoms compared to the control group. We will also compare conditions, as well as examine the impact of utilization. In exploratory analyses, we will examine to what extent changes in the ERN and error-sensitivity relate to changes in anxiety symptoms in children.

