5.0 Study Intervention

Description: As part of the current proposal, during Year 1, we 1.1 plan to develop a computerized intervention to be administered to parents and children separately. All participants in an active condition (parent/child, parent only, or child only) will receive the initial treatment session in the baseline lab visit. Additional materials that expand upon the concepts presented in the 1st session will be available online for children and parents between the baseline and follow-up assessment (depending on condition, e.g., in parent only condition, only parents will have access to between-session materials). These materials will include worksheets, games, and handouts. Participants will be told that participation in these additional online modules is optional and we will send a weekly reminder (via email or text) to remind them of concepts from the initial session, as well as provide the links to the additional materials. We will track utilization of the additional materials in parents and children. Additionally, as part of these additional modules, we will periodically ask parents and children to complete the Error Sensitivity Index to track changes across the 6 months between lab assessments. The development of this intervention, and testing its impact on ERN, is the primary goal of the proposed training grant. [name] is an expert in the area of computerized treatments for anxiety and will aid in the development and implementation of the intervention. Additionally, Drs. [name], [name], [name], and [name] all have expertise in intervention development and I will consult with them regularly during the development phase of the training grant. For the child intervention, we will use developmentally appropriate language, as well as stories that children between the ages of 5 and 7 can understand and relate to. We will train research assistants to guide children through the computer intervention and answer questions when children appear to be confused. We used this approach successfully when administering the Child Error Sensitivity Index to children between the ages of 5 and 7 years-old, as well as during pilot data collection. This intervention will be based on the constructs in the Child Error Sensitivity Index, as well as other constructs, that relate to the ERN – for example, perfectionism, fear of evaluation from others, and over-valuation of the negative consequences of errors. The intervention will focus on basic concepts such as: "making mistakes is how we learn new things", "everybody makes mistakes", and "good things come from mistakes." While the first session will focus primarily on constructs in the Child Error Sensitivity Index, the additional online materials will expand beyond this. For example, we will cover other constructs that may also relate to the ERN: e.g., tolerance of uncertainty, distress tolerance, mindfulness, constructive self-talk, facing fears, identifying sensations of anxiety, avoidance, behavioral inhibition, checking behavior, etc. - all in the context of, or relating to, performance monitoring or error sensitivity. The intervention will be

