For the control condition, we plan to utilize an active control previously used by [name]. This will be a computerized presentation, in the same format as the active intervention, but will focus on self-care topics – unrelated to error sensitivity. The computerized control presentation will be administered to both parents and children. Participants in the control condition will have access to online materials related to self-care between assessments. We view the current proposal as a first step in the development of a novel intervention targeting error sensitivity. If we are able to demonstrate initial target engagement (i.e., reduce the ERN), in future studies, we plan to examine the potential impact of dose and whether this intervention can provide incremental symptom reduction, in addition to existing treatment approaches for child anxiety.

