6.0 Procedures Involved*

6.1 We plan to recruit 175 parent/child dvads, high in error sensitivity (measured with self-report), and randomize 150 to an intervention condition (50 to parent/child, 50 to parent only, 50 to child only) and 25 to an active control condition. We plan to utilize an unbalanced design (150 intervention versus 25 controls) due to the fact that longitudinal data in developmental samples suggests the ERN is typically stable or increases across development. Therefore, a decrease in the ERN is not expected to occur in the control group. We will measure the ERN in children pre and post intervention, as well as error sensitivity and anxiety symptoms. At a six-month follow-up, we will again assess children's ERN, as well as error sensitivity and anxiety symptoms. We chose a six-month follow-up assessment to allow for adequate time for the parenting intervention to impact children (1-month may be too brief to observe impact), as well as to allow for children and parents to access the additional online materials (24 modules will be offered). This time was also selected to minimize drop-out that might occur over longer follow-up periods.

Further, before and during all in-person lab visits, we plan to take protective measures in order to reduce any possible spread of COVID-19 and to prevent any individuals at higher risk from participating in our study. Provided IRB approval, we plan to resume lab visits on August 1 with these protective measures in place.

6.2 Year 1: intervention development, collect pilot data from 10 parent/child dyads.

Year 2 - 4: recruit and collect data from 6 parent/child dyads per month, total N = 175 parent/child dyads. We will also collect 6-month follow-up data in the lab for each parent/child dyad.

Year 5: complete all follow-ups. Data processing, analysis, statistical procedures and manuscript preparation.

Risks are fairly minimal. There is a chance that some parents or children may experience mild, transient distress during parts of the assessments. All questions (self-report) are the type typically asked during a routine psychological or medical evaluations. If necessary, the assessment can be interrupted or terminated. The family (parent and patient) will be clearly informed that they are free to terminate participation at any point in the protocol.

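### Aim 2b and its repeats examine the impact of optional, self-selected module use by comparing heavier with lighter users; randomisation does not protect this comparison, so it should be stated and modelled as an association

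*Combined protocol and SAP*

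**What the plan says.** The sub-aim is worded as "2b. Examine the impact of utilization" (protocol 2.0, repeated in the data analysis plan at 17.1). Its only analytical content is the prediction "We expect that parents and children who utilize the treatment materials more frequently will experience the greatest reduction in the ERN". Aim 2c carries all hypotheses over to self-reported and observed error sensitivity. For anxiety symptoms, Aim 3 adds: "We will also compare conditions, as well as examine the impact of utilization".

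On how use arises, section 5.0 says "Participants will be told that participation in these additional online modules is optional and we will send a weekly reminder", and section 13.5 adds a t-shirt for completing the modules. The protocol describes no random variation in the reminder. Section 6.1 states that "24 modules will be offered". Section 5.0 makes access depend on condition: in the parent-only arm, for example, only the parent can reach the materials. Use will be recorded ("We will track utilization of the additional materials in parents and children"), but no metric is defined. In the control arm, "Participants in the control condition will have access to online materials related to self-care between assessments", and no use of that information is planned.

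Section 17.1 restates the aims. It gives no model, covariates or handling of confounding for utilization. Only the analysis relating change in the ERN and in error sensitivity to change in anxiety is called exploratory; 2b is not.

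**The concern.** Families decide how much to use the modules, and they decide after randomisation. Motivation, the child's anxiety, parenting style and outside treatment (which section 6.2 allows to begin during the study) may each affect both module use and the course of the ERN. Comparing heavier with lighter users mixes these influences with any effect of the modules.

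Two features of the design add to this. First, access differs by arm, so if arms are pooled without a term for arm, the amount of use carries information about arm. The combined arm is the one expected to do best in 2a, so a difference between arms could appear as a slope on use. Second, the randomised arm cannot be used to isolate the modules, because every active family also receives the session in the lab.

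At stake is what 2b, its extension in 2c and its repeat in Aim 3 may conclude. Worded as impact, a positive slope would be reported as a benefit of using more material, and a null slope as lack of benefit. Neither reading would be secure.

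**Working it through.** The documents give no model, effect size, alpha or power for 2b, so there is no figure of the plan's to reproduce. The check asks only whether self-selection could produce a significant slope when the modules do nothing.

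**Inputs from the documents.** 150 dyads in active arms and 25 controls (6.1). Retention of 90%, given as N = 155 (25.1). 0.90 × 175 = 157.5, and 155/175 = 88.6%, so the two figures agree closely. Active completers: 150 × 0.90 = 135, or 150 × 155/175 = 133.

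**Assumptions.** One unmeasured family factor correlates *a* with module use and *b* with ERN reduction; modules have no effect; two-sided alpha is 0.05. None of these values comes from the documents.

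**Formula.** The induced correlation is ρ = a × b. With z = atanh(ρ) × √(n − 3), the chance of a significant result is Φ(z − 1.96) + Φ(−z − 1.96). For n = 135, √132 = 11.49.

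| a (use) | b (ERN change) | ρ | z | chance of p < 0.05 |
|---|---|---|---|---|
| 0 | 0 | 0 | 0 | 5% |
| 0.3 | 0.1 | 0.03 | 0.34 | 6% |
| 0.2 | 0.2 | 0.04 | 0.46 | 7.5% |
| 0.5 | 0.1 | 0.05 | 0.58 | 9% |
| 0.3 | 0.3 | 0.09 | 1.04 | 18% |
| 0.4 | 0.4 | 0.16 | 1.85 | 46% |
| 0.5 | 0.5 | 0.25 | 2.93 | 84% |

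A simulation of 20,000 trials per scenario at n = 135 gave 7.5%, 17.8%, 46.0% and 83.8% for the four rows with a = b > 0. At n = 133 it gave 7.3%, 17.9%, 45.3% and 83.4%. When the common factor was fully measured and adjusted for, the rate was 4.7% to 5.2% throughout. That is the best case, since a proxy for motivation would remove only part of the bias.

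**Direction.** The table assumes that *a* and *b* have the same sign. If the families with most difficulty use the modules most, the signs differ and a real benefit could be masked.

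**Arm as a proxy.** The documents do not say whether the 24 modules are per person or per family. If each person has 24 and use is summed over the dyad, the ceiling is 24 + 24 = 48 in the combined arm and 24 in each single-person arm. Summed use would then be tied to arm by construction.

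**Could the control arm supply the answer?** Retained controls: 25 × 0.90 = 22.5, about 22. The standard error of the difference between two standardised slopes is about √(1/133 + 1/20) = 0.24, taking n − 2 in each group, so the 95% interval is about ±1.96 × 0.24 = ±0.47. For a true standardised slope of 0.3 in the active arms and none in controls, power for the difference is Φ(0.3/0.24 − 1.96) = Φ(−0.71) = 24%. Within the active arms alone it is Φ(0.3 × √133 − 1.96) = Φ(1.50) = 93%. The control slope is too imprecise to carry the interpretation.

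**The case against.** The strongest reply is that the plan records no faulty analysis. Section 17.1 names no model for any aim, does not say that the comparison will be unadjusted, and its prediction about frequent users is itself a statement of association. The causal reading rests on the word impact. This is fair as far as it goes. However, impact is the stated objective, the user comparison is the only analysis described for it, and nothing limits what may be concluded. The lack of a caveat or adjustment set is the gap to close.

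Second, the size is assumed. A correlation of 0.5 between a family trait and change in a neural difference score is strong, and with 0.1 on the ERN side the rate is only 6% to 9%. That stands. In addition, several plausible confounders are measured: the SCARED at baseline, and parenting instruments (PSDQ, CRPBI, CCNES) listed in 6.3. Adjustment can therefore remove part of the bias, with motivation as the main remainder.

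Third, a reader might infer that a positive 2b result would feed the later dose study. The documents do not support this. The control-condition text in section 5.0 makes that future work conditional on showing target engagement, that is, on reducing the ERN. It does not mention 2b.

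Fourth, a reader might think that only the excess of the active slope over the control slope should be interpreted. With an interval of about ±0.47, this would in effect remove 2b. Self-care material given to both parent and child is also an imperfect comparator for the single-person arms, and it may have effects of its own.

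**Conclusion.** The concern holds for the utilization analyses: 2b, its extension in 2c and its repeat in Aim 3. Use is self-selected and access depends on arm, so a difference between heavier and lighter users is not evidence of an effect of the modules, whichever way it points.

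The size of the bias cannot be derived from the documents. Under an assumed common factor, with 135 active dyads and no true effect, the false-positive rate runs from about 6% to 84%. The range shows that the problem can be negligible or severe. A reader might take the upper end as the expected error rate, but nothing in the documents supports that.

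Nor does the point reach the main comparisons. Aims 1, 2 and 2a contrast randomised arms and are unaffected.

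**What to change.** 1. Restate 2b, its extension in 2c and its repeat in Aim 3 as associations between module use and outcome, not as evidence of an effect of the modules.
2. Define utilization before analysis, for example modules used, recorded separately for parent and child, and state how the two are combined in the parent/child arm.
3. Fit the model within the active arms: month-6 ERN on modules used, adjusted for arm, pre-intervention ERN, baseline child and parent error sensitivity, baseline SCARED (stating which informant), the baseline parenting measures and age. Section 6.3 lists the parenting measures without visit times, so confirm that they are completed before the intervention.
4. Use the same structure for the 2c and Aim 3 outcomes, with the follow-up visit value as outcome. The interim Error Sensitivity Index is collected through the optional modules, so its availability itself depends on use.
5. State in the report that residual confounding by motivation remains and that the bias may run in either direction.
6. If control-arm use of the self-care modules is logged, report its slope with a confidence interval as a descriptive diagnostic only, not as the sole basis for interpretation.

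The cost is wording, a definition and one prespecified model using data the study already plans to collect. Logging control-arm use would be a small optional addition. The downside is a weaker claim for 2b.
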